**Protocol Identifying Number: SECURE-T2D**

**IDE G230013**

**IDE Sponsor: Insulet**

**Funded by: Insulet Corporation**

**Version Number: 3.2**

**27 February 2024**

## PROTOCOL SUMMARY

Title	Safety and Efficacy of the Omnipod® 5 Automated Insulin Delivery System in Adults with Type 2 Diabetes
Purpose	This single-arm, multi-center, prospective study will evaluate the safety (primary) and efficacy (secondary) of the Omnipod® 5 Automated Insulin Delivery System in adults with type 2 diabetes requiring insulin therapy.
Investigational Device	Omnipod® 5 Automated Insulin Delivery System, comprised of the following components: 
 
• Omnipod 5 Pod
 
• Omnipod 5 App (installed on the Insulet-provided Controller or smart phone)
 

Objectives	Primary Objective: 
 
• To evaluate the safety of the Omnipod 5 System in adults with type 2 diabetes.
 
 Secondary Objectives: 
 
• To evaluate the efficacy of the Omnipod 5 System in adults with type 2 diabetes.
 
• To evaluate glycemia measures of efficacy of the Omnipod 5 System and quality of life of Omnipod 5 System users.
 

Study Design	Single-arm, multi-center, prospective study
Number of Sites	~20-25 sites in the United States
Endpoints	Safety Primary Endpoint: Change in HbA1c at 13 weeks from baseline 
 
• Tested first for non-inferiority (non-inferiority limit 0.3%) and then if non-inferiority is demonstrated, tested sequentially for superiority
 
 Additional Safety Endpoints: 
 
1. Severe hypoglycemia
 
2. Hospitalization/ER for severe hypoglycemia
 
3. Hyperosmolar hyperglycemic syndrome (HHS)/ diabetic ketoacidosis (DKA)
 
4. Hospitalizations or ER related to hyperglycemia or hypoglycemia in the previous 3 months vs. study 3 months
 
5. Other related serious adverse events
 
6. Reportable device-related adverse events
 
 Additional Key Secondary Endpoints The following secondary endpoints will be tested hierarchically if the primary HbA1c analyses for non-inferiority followed by testing for superiority are statistically significant 
 
1. Mean glucose (superiority)
 
2. Change in % time 70-180 mg/dL (superiority)
 

	
 
3. Change in % time 70-140 mg/dL (superiority)
 
4. Change in % time <math>\geq</math> 300 mg/dL (superiority)
 
5. Change in % time <math>></math> 250 mg/dL (superiority)
 
6. Change in % time <math>></math> 180 mg/dL (superiority)
 
7. % time <math><</math> 70 mg/dL (noninferiority; margin = 2.0%)
 
8. % time <math><</math> 54 mg/dL (noninferiority; margin = 0.5%)
 
9. T2-DDAS total score (superiority)
 
10. Change in % T2-DDAS total score <math>></math> 5.0 (high distress)
 
11. PSQI total score (superiority)
 
12. Change in % PSQI total score <math>\geq</math> 2.0 (poor sleep)
 
13. HCS total score (superiority)
 
14. Change in HCS total score <math><</math> 3.0 (low confidence)
 
15. % time <math><</math> 70 mg/dL (superiority)
 
16. % time <math><</math> 54 mg/dL (superiority)
 
17. Coefficient of variation (superiority)
 

Population	
Inclusion Criteria:
 
Participants must meet all of the following criteria to be included in the study:
 
 
1. Age at time of consent 18-75 years
 
2. Diagnosed with type 2 diabetes, on current insulin regimen for at least 3 months prior to screening (i.e. Basal-bolus, basal only or pre-mix)
 
3. Basal bolus (long-acting insulin and rapid acting analog) or pre-mix users with A1C <math><</math> 12.0% OR basal users on long or intermediate acting insulin only with A1C <math>\geq</math> 7.0% and <math><</math> 12.0%
 
4. Willing to use only the following types of U-100 insulin during the study: Humalog U-100, Novolog, or Admelog
 
5. Participant agrees to provide their own insulin for the duration of the study
 
6. Stable doses over the preceding 4 weeks of other glucose-lowering medications as determined by Investigator
 
7. Stable doses of weight loss medications over the preceding 4 weeks and throughout the study that may affect glycemic control directly and/or indirectly, except for a dose reduction or discontinuation, as determined by Investigator
 
8. Willing to wear the system continuously throughout the study
 
9. Deemed appropriate for pump therapy per investigator's assessment considering previous history of severe hypoglycemic and hyperglycemic events, and other comorbidities
 
10. Investigator has confidence that the participant has the cognitive ability and can successfully operate all study devices and can adhere to the protocol
 
11. Able to read and understand English or Spanish
 
12. Willing and able to sign the Informed Consent Form (ICF)
 
13. If female of childbearing potential, willing and able to have pregnancy testing
 
 
Exclusion Criteria:

	
Participants who meet any of the following criteria will be excluded from the study:
 
 
1. Use of an AID pump in automated mode within 3 months prior to screening
 
2. Any medical condition which in the opinion of the investigator, would put the participant at an unacceptable safety risk, such as untreated malignancy, unstable cardiac disease, unstable or end-stage renal disease, and/or eating disorders (i.e. anorexia/bulimia)
 
3. Current or known history of coronary artery disease that is not stable with medical management, including unstable angina, or angina that prevents moderate exercise despite medical management, or a history of myocardial infarction, percutaneous coronary intervention, or coronary artery bypass grafting within the 12 months prior to screening
 
4. Any planned surgery during the study which could be considered major in the opinion of the investigator
 
5. History of more than 1 severe hypoglycemic event in the 6 months prior to screening
 
6. History of more than 1 episode of diabetic ketoacidosis (DKA) or Hyperosmolar hyperglycemic syndrome (HHS) in the 6 months prior to screening; unrelated to an intercurrent illness; kinked, dislodged, or occluded cannula; or initial diabetes diagnosis
 
7. Blood disorder or dyscrasia within 3 months prior to screening, including use of hydroxyurea, which in the investigator's opinion could interfere with determination of HbA1c
 
8. Plans to receive blood transfusion over the course of the study
 
9. Has taken oral or injectable steroids within 8 weeks prior to screening or plans to take oral or injectable steroids during the study
 
10. Unable to tolerate adhesive tape or has any unresolved skin condition that could impact sensor or pump placement
 
11. Pregnant or lactating, planning to become pregnant during the study, or is a woman of childbearing potential and not on acceptable form of birth control (acceptable includes abstinence, condoms, oral/injectable contraceptives, IUD, or implant); childbearing potential means that menstruation has started, and the participant is not surgically sterile or greater than 12 months post-menopausal)
 
12. Participation in another clinical study using an investigational drug or device other than the Omnipod 5 in the 30 days prior to screening or intends to participate during the study period
 
13. Unable to follow clinical protocol for the duration of the study or is otherwise deemed unacceptable to participate in the study per the investigator's clinical judgment
 
14. Participant is an employee of Insulet, an Investigator or Investigator's study team, or immediate family member (spouse, biological or legal guardian, child, sibling, parent) of any of the aforementioned
 

Sample Size	Up to 400 screened participants to provide a cohort of 300 initiating use of the Omnipod 5 system and at least 275 completing the trial. A minimum of 60 and maximum of 125 participants using basal only.
Treatment Groups	Single-arm intervention that consists of 13 weeks of treatment using the Omnipod 5 System

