Statistical Methods	
A hierarchical testing scheme will be used to test for statistical significance of the change in the primary and key secondary outcomes listed above over 13 weeks of treatment.
 
The primary outcome of interest is HbA1c. Change in HbA1c will be tested for non-inferiority, comparing the HbA1c results from the Standard Therapy period to the Treatment period; if non-inferiority is established, superiority will be tested. The details are as follows:
 
 
Non-inferiority test for mean change in HbA1c from the Standard Therapy period to the Treatment period (e.g., HbA1cTreatment - HbA1cStandard = <math>\mu_{\delta}</math>) at alpha=0.025 with non-inferiority margin on 0.3%.
 
Superiority test (two-sided) for <math>\mu_{\delta} = 0</math> at alpha=0.05.
 
 
Summary statistics appropriate to the distribution will be generated for the Standard Therapy and Treatment periods, as well as for the difference (HbA1cTreatment – HbA1cStandard).
 
A paired t-test will be used to compare the change in HbA1c from Standard Therapy to the end of the Treatment periods. It is expected the change in HbA1c will follow a relatively normal distribution. If not normally distributed, robust regression using M-estimation with the Huber weight function will be used instead of a pair t-test. A point estimate and 95% confidence interval will be given for the mean change in HbA1c from baseline to 13 weeks.
 
If statically significant results (i.e., <math>p \geq 0.05</math>) are obtained for the primary endpoints, the key secondary outcomes will be tested hierarchical in the order listed above. If any of the key secondary outcomes fail to give a statistically significant result, then formal testing will stop and p-values will not be given for any outcomes further down on the list. Summary statistics and confidence intervals will be given for each outcome regardless of statistical significance. Note that each of the CGM metrics in the hierarchical listing refers to the overall 24-hour version.
 
All adverse events and additional safety outcomes listed above will be tabulated for each period (Standard Therapy and Treatment). The number of events and event rate per 100 person-years during the Treatment period will also be calculated.

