## Insulet

	
McNemar's test will be used to compare the percentage of participants with hospitalization or ER visits related to hyper- or hypoglycemia during the 13-week Treatment period compared with the 13-week period prior to enrollment.
 
All variables will be examined for normality of their distributions and, if applicable, standard residual diagnostics will be performed. If values are highly skewed, then a nonparametric or robust regression M-estimation method will be used instead.

--	---

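### Do the three questionnaire cut-off steps (10, 12 and 14) wrongly block formal testing of hypoglycemia and CV superiority at steps 15 to 17?

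*Combined protocol and SAP*

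**What the plan says.** The Endpoints row of the Protocol Summary lists 17 key secondary endpoints, reached only if HbA1c non-inferiority and then superiority are both significant. Steps 1 to 6 are glycemic superiority tests. Steps 7 and 8 are non-inferiority tests of time <70 and <54 mg/dL, with margins of 2.0% and 0.5%.

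The questionnaires follow in pairs. Step 9 is "T2-DDAS total score (superiority)" and step 10 is "Change in % T2-DDAS total score > 5.0 (high distress)". Steps 11 and 12 do the same for the PSQI total (cut-off at 2.0 or above, poor sleep). Steps 13 and 14 do so for the HCS total, where step 14 reads "Change in HCS total score < 3.0 (low confidence)". Steps 15 to 17 are superiority for time <70 mg/dL, time <54 mg/dL and CV.

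The Statistical Methods row sets the rule: "If any of the key secondary outcomes fail to give a statistically significant result, then formal testing will stop". It adds: "Summary statistics and confidence intervals will be given for each outcome regardless of statistical significance". The Sample Size row plans for "at least 275 completing the trial".

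**The concern.** Each cut-off step uses the score tested just before it and discards information. Under a simple shift in the mean, the categorised test has less power than the score test. Here it is not an optional extra, because failure at step 10, 12 or 14 ends formal testing. A device that did reduce hypoglycemia could lose its superiority claims for time <70 and <54 mg/dL, and for CV, because too few participants crossed a distress, sleep or confidence threshold.

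The drafting adds to the unease. Steps 10, 12 and 14 are the only three of the 17 with no superiority or non-inferiority label. Step 14 lacks the percent sign that steps 10 and 12 carry. No test is named for the three; the only paired-proportion test in the text belongs to another outcome: "McNemar's test will be used to compare the percentage of participants with hospitalization or ER visits".

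**Working it through.** **1. Is there a stated figure to reproduce?** No. The Protocol Summary gives no power, effect size, SD, correlation, category prevalence or score range for steps 9 to 17. The only usable input is n = 275. Everything else below is assumed.

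**2. Does the order harm type I error?** No. In a fixed sequence a false claim requires rejection of the first true null hypothesis in the list. That one test has error probability at most alpha, whatever precedes it. I take alpha as two-sided 0.05 at each superiority step; the text states this for HbA1c superiority only. Adding, removing or moving steps 10, 12 and 14 does not change the bound.

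**3. How much power might the cut-offs cost?** Assume scores before and after treatment are bivariate normal with correlation 0.6 and a pure shift of *d* SDs of change. In baseline SDs the shift is d × √(2(1 − 0.6)) = 0.894d.

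- Score test: paired t-test with noncentrality d√275 = 16.58d. For d = 0.197, power is 0.902, and three independent scores give 0.902³ = 0.73.
- Category test: McNemar, with power approximately Φ[(δ√n − 1.96√ψ)/√(ψ − δ²)]. Here ψ is the proportion changing category and δ the net difference.
- Example, d = 0.30 and baseline prevalence 30%: 16.5% leave the category and 7.9% enter it, so ψ = 0.243 and δ = 0.086. Power is about Φ[(0.086 × 16.58 − 1.96 × 0.493)/0.486] ≈ 0.83. With the exact test, simulation gives 0.805 for passing both score and category, and 0.805³ = 0.52.

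Chance of clearing all of steps 9 to 14 (exact McNemar, three independent questionnaires, 50,000 simulated trials per cell for the category columns):

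| d | Scores only | 50% prevalence | 30% | 10% | 90% |
|---|---|---|---|---|---|
| 0.197 | 73% | 14% | 9% | 1% | 2% |
| 0.30 | about 100% | 68% | 52% | 9% | 23% |
| 0.40 | about 100% | 96% | 89% | 31% | 67% |
| 0.50 | about 100% | about 100% | 99% | 60% | 95% |

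The result moves with every assumption:

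- At d = 0.30, correlations of 0.4 and 0.8 give 81/67/15% and 42/29/3% at prevalences of 50/30/10%.
- If the three questionnaires were fully dependent, the d = 0.197 row becomes about 51/45/22%, against 90% for scores only.
- Prevalence of 90% is not the mirror image of 10%, because improvement then moves participants towards the dense part of the distribution.

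**4. Is there a point at which a step cannot succeed?** Yes. With exact McNemar, five changes all in one direction give 2 × 0.5⁵ = 0.0625, and six give 2 × 0.5⁶ = 0.031. Fewer than six changers (6/275 = 2.2%) cannot be significant. Nothing in the documents suggests that so few would change.

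**5. What is lost if testing stops at step 10, 12 or 14?** Formal p-values for later steps only. HbA1c and steps 1 to 9, including hypoglycemia non-inferiority at steps 7 and 8, are already settled. Estimates and confidence intervals for steps 15 to 17 are still reported.

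**6. What would dropping the three steps buy?** The order 9, 11, 13, 15, 16, 17 gives up formal claims on high distress, poor sleep and low confidence. Steps 15 to 17 would still wait on three questionnaire scores. Moving the categories after step 17 would make those claims wait on CV superiority instead. Either way, some claims become easier to reach at the expense of others.

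**The case for a change.** The strongest case for the concern is that the structural part needs no assumptions: the order and the stop rule are explicit, and the text gives no reason for making three glycemic claims depend on categorised repeats of scores just tested. The cut-off test was also weaker than the score test in every scenario tried, across correlations of 0.4 to 0.8 and prevalences of 5% to 90%. Replacing exact McNemar with the uncorrected asymptotic version does not remove the gap; at d = 0.30 it gives 72/59/16% at prevalences of 50/30/10%. The change would need only wording.

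All of that stands as a description of a trade-off. It does not show an error. A category answers a different question from a mean (how many people leave high distress), and the Objectives row names quality of life as a secondary objective. A sponsor may reasonably rank those claims above late superiority claims on hypoglycemia and CV. The missing labels, the missing test and the percent sign in step 14 are fair requests for detail, but they do not show that the sequence is wrong. The text supplied is also a summary, so a test not named there is weak evidence about the full plan. Whether the cut-offs suit their instruments cannot be judged without score ranges, which the documents do not give.

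**Conclusion.** The concern does not hold. The plan states an order and a stop rule, the two are consistent, and together they control type I error. No stated power or other figure is missed. The possible loss is confined to formal p-values at later steps, chiefly the superiority claims at 15 to 17. Its size cannot be fixed from the documents: under the model above, the chance of clearing steps 9 to 14 runs from about 1% to about 100%, depending on effect size and prevalence. That rests on normal scores, a pure mean shift, correlation 0.6, equal effects, independent questionnaires and 275 completers, of which only the last is in the plan. A stop at steps 10, 12 or 14 is possible but not shown to be likely. Whether to keep the categories there is a choice of priorities on which reasonable statisticians would differ.

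### Does inclusion criterion 7 leave open whether participants whose drugs change after entry stay in the primary HbA1c test?

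*Combined protocol and SAP*

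**What the plan says.** All references are to the Protocol Summary.

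- **Population, lead-in to the inclusion criteria:** "Participants must meet all of the following criteria to be included in the study".
- **Criterion 7, weight-loss drugs:** "Stable doses of weight loss medications over the preceding 4 weeks and throughout the study", then the exception: "except for a dose reduction or discontinuation, as determined by Investigator".
- **Criterion 6, other glucose-lowering drugs:** "Stable doses over the preceding 4 weeks of other glucose-lowering medications as determined by Investigator". It sets nothing for the period after entry.
- **Criteria 4, 5 and 8** also look ahead, but are worded as willingness or agreement: "Willing to use only the following types of U-100 insulin during the study"; "Participant agrees to provide their own insulin for the duration of the study"; "Willing to wear the system continuously throughout the study".
- **Exclusion criterion 13** turns on inability to follow the protocol for its whole duration, or other unsuitability in the investigator's judgement.
- **Statistical Methods:** "Non-inferiority test for mean change in HbA1c from the Standard Therapy period to the Treatment period", at alpha 0.025 with a 0.3% margin, then a two-sided superiority test at 0.05. The method is a paired t-test, with Huber M-estimation if the changes are not normally distributed. No analysis set is named and drug changes are not mentioned.
- **Sample Size:** 300 starting the system and at least 275 completing.

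**The concern.** Criterion 7 is the only inclusion criterion worded as a fact about the treatment period. Taken literally, it cannot be verified at entry and can be failed later. The exception makes that failure one-sided: a participant who reduces or stops a weight-loss drug still satisfies it, and one who increases it does not.

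If failing the criterion meant leaving the primary analysis, the sample would depend on something that happens after treatment starts and may follow from the response to treatment. If increases follow poor response, dropping those participants flatters the device. If the increases themselves lowered HbA1c, dropping them counts against it. If the reading were settled with HbA1c in view, the analyst would be choosing the sample.

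The HbA1c change carries both the non-inferiority and the superiority conclusions and opens a hierarchy of 17 key secondary endpoints. There is also a separate question of attribution. With no control arm, any drug change during treatment becomes part of the observed mean change, and criterion 6 sets no limit on such changes after entry.

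**Working it through.** **Step 1. Is there a removal rule?** The lead-in governs inclusion in the study, which is eligibility and not membership of an analysis set. The summary contains no per-protocol set, no exclusion for drug changes and no withdrawal from analysis after entry. Exclusion 13 is the closest match in form to criterion 7: it too is a statement about the future that can only be settled at entry, by investigator judgement. Criterion 7 also ends by leaving the matter to the investigator. Read with its neighbours, it is an expectation at entry. A paired t-test stated without exclusions uses every participant with a baseline and a week-13 HbA1c.

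**Step 2. What would removal do, if it happened?** The plan gives no figure to reproduce here beyond attrition: (300 - 275)/300 = 25/300 = 8.3%. Everything else is assumed: share removed f, correlation rho between a drug increase and poor response, HbA1c reduction d from the increase, and SD of change s.

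Fix the true mean change in all 300 starters at zero. After removal:

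- mean in those left = f·d - s·rho·k, with k = phi(z_f)/(1 - f)
- one-sided rejection rate = Phi(-mean/(s/sqrt(300(1 - f))) - 1.96)

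Worst case shown, f = 25/300, rho = 0.5, d = 0, s = 1.0:

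- k = 0.1533/0.9167 = 0.167
- mean = -0.5 × 0.167 = -0.0836
- SE = 1/sqrt(275) = 0.0603
- rate = Phi(0.0836/0.0603 - 1.96) = Phi(-0.57) = 28.3%; simulation (60,000 trials) gives 29.6%

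Simulated one-sided rejection rates (nominal 2.5%, SD 1.0):

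| Removed | d | rho 0.3 | rho 0.5 |
|---|---|---|---|
| 2% | 0 | 4.4% | 6.2% |
| 5% | 0 | 8.1% | 15.4% |
| 8.3% | 0 | 13.0% | 29.6% |
| 8.3% | 0.5 | 3.5% | 10.5% |
| 8.3% | 1.0 | 0.6% | 2.6% |

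At rho = 0 there is no inflation. With d = 1.0 and 8.3% removed, removal instead costs power: for a true 0.2-point fall it drops from 91.5% to 48.8%. With everyone kept, the rate is 2.35-2.65% in all 27 cases run.

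**Step 3. The same model with a different null.** Step 2 fixes the total mean change at zero, drug effect included. Now set the device effect at zero and keep everyone, with f = 25/300, d = 1.0, s = 1.0, rho = 0:

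- shift in favour of the device = f·d = 0.0833
- SE = sqrt((1 + f(1 - f)d²)/300) = sqrt(1.0764/300) = 0.0599
- rate = Phi(0.0833/0.0599 - 1.96) = Phi(-0.57) = 28%

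Simulation gives 28, 31 and 32% at rho 0, 0.3 and 0.5. Removal gives 2.6, 13 and 30% in the same cases. At d = 0.5, keeping everyone gives about 11%.

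Which handling looks worse therefore depends on whether the target is the mean change or the change due to the device alone. Neither isolates the device effect. The parameter the plan tests is the mean change, and for that parameter keeping everyone is the valid choice.

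**The case for a change.** The strongest case for acting is that the text does not compel the benign reading. The lead-in says the criteria must be met, criterion 7 alone among the inclusion criteria is worded as a fact about follow-up, and no analysis set is stated. The primary endpoint is a safety conclusion in a study without a control arm. A sentence fixing the analysis set, plus a table of drug changes, would cost almost nothing and would shut out a choice made after the data are seen.

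The description of the wording stands, and the calculations reproduce. The inference does not.

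- Removal is nowhere in the summary, so the inflated error rates measure an invented step.
- The inputs are stretched. On the literal reading only increases (or starts) of weight-loss drugs would fail criterion 7, and the summary does not say how many participants take such drugs. An 8.3% removal rate uses up the whole gap between 300 and 275 and leaves nothing for ordinary losses.
- The analysis set that the sentence would state is the one the plan already gives on a plain reading.
- Only the summary is at hand. Analysis sets and the recording of concomitant drugs usually belong in the body of a protocol, so silence here is weak evidence of an omission.
- Criteria 6 and 7 cover differently described drug groups. Different windows are uneven but not contradictory.

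The attribution point is real, but neither the extra sentence nor the table would remove it.

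**Conclusion.** No change to the plan follows. Criterion 7 is loosely worded and the summary names no analysis set, but the ordinary reading is clear: eligibility is judged at entry, and the primary test uses everyone with both HbA1c values, whatever happens to their other drugs. An analyst following the text would already do what a correction would ask for.

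The figure of about 28-30% depends on removal of participants, which the plan does not provide for, and on assumed values of 8.3% removed, rho 0.5 and no drug effect by week 13. It should not be presented as a property of this design. Under the plain reading the one-sided error for the mean change stays at its nominal 2.5%.

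What remains is a limit on interpretation. If 5-8.3% of participants increased a drug, the mean change would include 0.025-0.042 points in the device's favour at an assumed 0.5-point effect (0.05 × 0.5; 0.083 × 0.5), or 0.05-0.083 at 1.0 point. That comes with any single-arm before-after comparison. This conclusion assumes that the body of the protocol contains no rule removing participants from the primary analysis for drug changes; such a rule would reopen the question.
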